Study Design	Randomized-controlled clinical trial. Patients will be enrolled within 4 days of mechanical ventilation and randomized 1:1 to titration of PEEP based on esophageal balloon pressures or based on the "High PEEP" ARDSnet PEEP/FiO ₂ table. All patients will have esophageal balloons placed with baseline measurement of Ptp. Patients randomized to the intervention arm will then undergo titration of PEEP based on Ptp measurements to achieve "Optimal PEEP," defined as end expiratory Ptp of 0 to +2 cm H ₂ O.

Subject Population key criteria for Inclusion and Exclusion:	
Inclusion Criteria: Obese adults (BMI ≥ 40) admitted to the medical ICU at UNC Hospitals or Vidant Medical Center at ECU with acute respiratory failure requiring mechanical ventilation.
 
Exclusion Criteria:
 
 1. Refusal to give consent by subject or LAR 2. Abdominal compartment syndrome 3. Chest tube for pneumothorax 4. Having been on a ventilator for >4 days 5. Suspicion of or known intracranial hypertension 6. Anticipated extubation within 24 hours 7. Chronic ventilator dependence 8. Condition that precludes placement of an esophageal balloon (esophageal or nasopharyngeal pathology preventing insertion of the esophageal balloon catheter, severe thrombocytopenia, or coagulopathy) 9. Incarceration 10. Not expected to survive >48 hours 11. Unable to obtain consent from subject or LAR 12. Unable to obtain consent due to a language barrier
Number Of Subjects	76 patients
Study Duration	Each subject's participation will last for up to 28 days. The entire study is expected to last about 12-24 months.
Study Phases	
(1) Screening: Screening for eligibility and obtaining consent for enrollment.
 
(2) Pre-Intervention: Esophageal balloon placed and baseline data collected.
 
(3) Intervention: PEEP titrated to achieve Optimal PEEP in the intervention group. Ptp Measurements will be obtained daily and adjustments to PEEP will occur daily.
 
(4) Subject Completion/Withdrawal: Study will conclude for each patient at 28 days after enrollment or hospital discharge.

Efficacy Evaluations	Primary evaluation measurements that will be used to assess the efficacy of the intervention are ventilator free days at day 28. Differences between control and intervention groups will be attributed to differences in PEEP management.

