Safety Evaluations	Periodic review will be performed by the NC TraCS DSMB. They will review aggregate safety data after 25, 50, and 75% enrollment to ensure there are not safety differences between the groups in hypotension requiring vasopressors and development of pneumothorax. All patients will have

continuous monitoring of HR, BP, and oxygenation per ICU protocol to monitor patient safety.

Statistical And Analytic Plan

This is a randomized, controlled trial to evaluate the effect of using Optimal PEEP based on an esophageal balloon measurement on duration of mechanical ventilation. We hypothesize that using Ptp to identify optimal PEEP will reduce time on the ventilator and therefore increase the ventilator free days at day 28. The primary outcome is the number of ventilator-free days, defined as the number of days alive and ventilator-free by day 28. Differences between the two groups in the primary outcome will be analyzed using independent t-tests and a linear regression model adjusting for BMI, abdominal girth, and Ptp.

DATA AND SAFETY MONITORING PLAN

The PI will be responsible for maintaining patient data and ensuring accuracy of the data collected. All patient data will be collected using REDCap through the NC TraCS system. REDCap allows for immediate data validation and range setting to reduce the likelihood of erroneous data entry. Data created for analysis will be de-identified and secured on a password protected UNC School of Medicine network hard drive. All investigators will be trained on completing the electronic case report form.

Patient safety will be monitored with continuous cardiovascular monitoring by the critical care team. Subject stopping rules will be in place to end the study intervention, including refractory hypotension, development of pneumothorax, or changes in oxygenation or hemodynamics that the primary team feels may be related to changes in PEEP.

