3 INVESTIGATIONAL PLAN

3.1 Study Design

We will conduct an open label randomized controlled clinical trial to evaluate the impact of titration to Optimal PEEP compared to use of a standardized PEEP table on the duration of mechanical ventilation in obese patients with acute respiratory failure. Patients will be followed for 28 days to evaluate for ventilator-free days. Blinding of the clinical team will not be possible due to the differences in treatment approach, including the performance of spontaneous breathing trials.

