3.3 Study Duration, Enrollment and Number of Participants

Enrollment will continue until 38 participants have been enrolled in each group (76 participants total). The medical ICU (MICU) admits approximately 150 per month, 40-50% of whom require mechanical ventilation. Based on a previous evaluation of lung protective ventilation in our hospital, approximately 45% of our patients requiring mechanical ventilation have a BMI ≥ 40 . Therefore, the MICU conservatively admits approximately 24 patients a month that meet inclusion criteria. Based on expected enrollment of at least 3-4 participants per month, the trial is expected to complete enrollment within 24 months. Each patient's participation will last 28 days or until death or hospital discharge.

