4.4 Participant Completion/ Withdrawal

Participants will complete the study at the time of death or the conclusion of 28 days, whichever occurs first.

Early completion of the trial for each participant will occur if any of the following outcomes are met:

- a. Patient or family withdraw consent for the study
- b. The clinical team feels that the patient no longer meets appropriateness for the study
- c. Patient develops an adverse effect felt possibly related to the intervention (refractory hypotension, nasopharyngeal bleeding, pneumothorax, etc)

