6.2 Statistical Methods

All continuous variables (see 5.2) will be described using mean and standard deviation, with associated 95% confidence intervals, or median with interquartile range as appropriate based on normality of distribution. All categorical variables will be described with frequency and percentage.

To determine if the optimal PEEP has an effect on the duration of mechanical ventilation compared to usual PEEP, the primary outcome will be analyzed with a 2-sided independent t-test. As secondary analysis, the associations between the primary outcome and exposures and demographic variables will be further analyzed using linear regression models.

The impact of optimal PEEP vs standardized PEEP titration will be assessed on all other variables with independent t-tests or chi-square tests as appropriate. All secondary outcomes, as described in 5.2, will be further analyzed with either linear regression models or logistic models, using demographic and exposure variables as predictors.

All tests will be 2-sided, and p-values < 0.05 will be considered significant. Tests with p-values above 0.05 will be considered inconclusive. Missing values will be ignored.

No interim analyses for efficacy or futility are planned, but interim analyses will be conducted for safety.

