7.2 Data and Safety Monitoring Plan

All participants will be continuously monitored by critical care nurses under the guidance of critical care physicians per individual ICU protocols.

Stopping rules and procedures

Subject stopping rules will be the development of any of the following after randomization:

- New pneumothorax
 - Pneumothorax is a known risk factor for all patients requiring mechanical ventilation with a case rate of <1% of all mechanically ventilated patients. In previous studies of optimal PEEP determination using esophageal balloon-guided pressure measurement, no pneumothoraces were observed. We believe the study procedures will be safe for both arms, and that the intervention arm will be at lower risk for this outcome. However, development of a pneumothorax will necessitate a chest tube and will invalidate the measurement of pleural pressure. Therefore the study procedures must be stopped.
- Epistaxis requiring intervention
 - In the event of epistaxis requiring packing or intervention, the esophageal balloon will be removed and the study subject's participation in the study will end.
- Hypotension
 - In the event a patient experiences a drop in mean arterial pressure (MAP) below 65 mm Hg or a significant change in vasoactive medication requirement (>10 mcg/min dose of norepinephrine equivalent), that is felt by the clinical ICU team to possibly be related to the intervention, the study subject's PEEP will be dropped by 2 cm H₂O every 5 minutes until the parameter returns to an acceptable range (as determined by the clinical ICU team) or until the PEEP reaches the pre-intervention level. The patient will remain on no higher than this new PEEP for the remainder of the study.

Adverse Event Reporting

All Adverse Events will be documented and graded using CTCAE grading, defined as any patient who develops one of the following (by CTCAE grading):

- grade 3-5 hypotension
- grade 2-5 pneumothorax
- grade 2-5 epistaxis

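### Follow-up can end before day 28, missing values are to be ignored and no as-randomised analysis is stated, so the primary comparison may be a biased complete-case test

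*Combined protocol and SAP*

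**What the plan says.** **Analysis.** Section 6.2 compares VFD between arms with a two-sided independent t-test. Its whole provision for missing data is "Missing values will be ignored". There is no exception for the primary outcome, no imputation and no sensitivity analysis. No section names an analysis set or says that patients are analysed as randomised. Section 6.3 raises 34 per group to 38 for 10% dropout.

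**End of follow-up.** Section 3.1 states: "Patients will be followed for 28 days to evaluate for ventilator-free days". Section 4.4 states: "Participants will complete the study at the time of death or the conclusion of 28 days, whichever occurs first". The Synopsis (Study Phases) instead states: "Study will conclude for each patient at 28 days after enrollment or hospital discharge". Section 3.3 says that "participation will last 28 days or until death or hospital discharge".

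**Early exit.** Section 4.4 lists three routes to early completion: withdrawal of consent, the clinical team's view that the patient is no longer suitable, and "Patient develops an adverse effect felt possibly related to the intervention (refractory hypotension, nasopharyngeal bleeding, pneumothorax, etc". The Synopsis (Data and Safety Monitoring Plan) treats two of those events as ending treatment only: "Subject stopping rules will be in place to end the study intervention, including refractory hypotension, development of pneumothorax". Section 7.2 ends participation for epistaxis that needs intervention, stops study procedures for pneumothorax, and for hypotension lowers PEEP and continues: "The patient will remain on no higher than this new PEEP for the remainder of the study".

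**Outcome source.** Section 5.2 takes VFD from the electronic medical record (EMR) at completion. Section 6.1 has a blinded team member assess it after the subject has completed.

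**The concern.** The t-test is protected by randomisation only if every randomised patient contributes a value. Here completion can come early, VFD is scheduled at completion, no section requires ventilator status after an early exit, and missing values are dropped. Followed literally, these rules can remove patients from the primary comparison.

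The removals need not be neutral. One exit is triggered by an effect attributed to the intervention. Another is the opinion of clinicians who know the arm, because the trial is open label. Both are plausibly linked to a poor course on the ventilator. If the intervention arm loses its worse patients and control keeps its own, the intervention looks better than it is.

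Discharge is a separate problem. With a mean of 7 ventilator days assumed in 6.3, many patients could leave hospital before day 28, and no rule says how their later days count. The direction of any bias from this route is not established.

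**Working it through.** **1. The plan's own figure.** Inputs from 6.3 are SD 2.9 days, a 2-day difference, 80% power and two-sided alpha 0.05. The noncentral-t solution is 33.99, so 34 per group, as stated. Dropout: 34 / 0.90 = 37.8, so 38 per group and 76 in total, as stated. Power for 2 days is 84.3% with 38 per group analysed and 80.0% with 34. The allowance shows that some patients were expected not to contribute.

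**2. Which events end what.**

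| Event | 4.4 | Synopsis | 7.2 |
|---|---|---|---|
| Pneumothorax | ends the trial for the patient | ends the intervention | stops study procedures |
| Hypotension | ends the trial (refractory) | ends the intervention (refractory) | stays in the study at capped PEEP |
| Nasal bleeding | ends the trial | not named | ends participation (epistaxis needing intervention) |
| Discharge | not an end point | ends the study | not addressed |

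In none of these is outcome collection said to continue. Staff working from different sections could handle the same patient differently.

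**3. Bias under assumed losses.** The documents give no early-exit rate by arm and no VFD for such patients, so both are assumed. Take 38 per arm and no true effect. In each arm, *k* patients have VFD averaging *d* days below the rest; within each subgroup the SD is 2.9.

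- Intervention drops its *k*, control drops none. The full-arm mean is μ − (k/38)d and the mean after dropping is μ, so bias = (k/38) × d.
- Intervention drops 4, control drops 2 of its 4: bias = (2/36) × d.
- Both arms drop the same number of comparable patients: bias = 0.

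The false-benefit rate is the share of 40,000 simulated trials with two-sided p < 0.05 in favour of the intervention (nominal 2.5%).

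| Loss | d = 3 | d = 10 | d = 20 |
|---|---|---|---|
| Equal in both arms | 0 days; 2.5% | 0 days; 2.5% | 0 days; 2.5% |
| 1 of 38, intervention only | 0.08 days; 3.2% | 0.26 days; 4.2% | 0.53 days; 4.3% |
| 2 of 38, intervention only | 0.16 days; 4.0% | 0.53 days; 7.0% | 1.05 days; 8.4% |
| 4 of 38, intervention only | 0.32 days; 6.0% | 1.05 days; 16.6% | 2.11 days; 27.0% |
| 4 intervention, 2 control | 0.17 days; 4.1% | 0.56 days; 7.1% | 1.11 days; 7.9% |

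A repeat run agreed to within about 1 percentage point. Four of 38 is about the 10% allowance and is an upper case. Limiting VFD to 0–28 lowers the largest bias by 0.03 to 0.08 days, depending on where the mean is centred.

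**4. What cannot be recovered afterwards.** Suppose the observed means are 23 and 21 VFD with 4 of 38 missing in each arm. Setting missing values to the extremes:

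- Worst case: (34 × 23 + 4 × 0)/38 − (34 × 21 + 4 × 28)/38 = 20.58 − 21.74 = −1.2 days.
- Best case: (34 × 23 + 4 × 28)/38 − (34 × 21 + 4 × 0)/38 = 23.53 − 18.79 = +4.7 days.

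An observed 2-day benefit would then not settle even the sign, so collecting the data matters more than any later adjustment.

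**The case against.** The strongest reply is that this reads silence as exclusion. The missing-data sentence is general and affects the primary outcome only if VFD is actually missing. VFD comes from the medical record, 3.1 intends 28-day follow-up, death is part of the outcome definition, and no per-protocol set is written. It stands that VFD need not be missing after an early exit. It does not close the gap, because no section requires the look-up, four sections limit follow-up or participation, and the hospital record may not show events after discharge.

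A second reply is that exits will be few. Section 7.2 puts pneumothorax below 1% of ventilated patients (under 0.01 × 38 = 0.4 per arm) and reports none in previous balloon-guided studies. Section 7.1 cites a small trial with no adverse effects. Both arms receive the balloon, and the consent and clinical-judgement routes apply to both. This stands: the low-loss rows deserve at least as much weight as the four-patient rows. Epistaxis, judgement and consent exits, however, have no stated rate.

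Third, the d = 20 column is extreme. With four such patients, the full-arm SD is √(2.9² + (4/38)(34/38) × 20²) = 6.8, far from the planned 2.9. That is fair, and the column is only an upper end.

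Finally, the hypotension conflict is softer than the others. Section 4.4 and the Synopsis speak of refractory hypotension, while 7.2 describes a pressure or vasopressor trigger. These may be different states, although 7.2 also covers the patient whose PEEP returns to its starting level without recovery.

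**Conclusion.** The concern holds. As written, the plan permits a complete-case primary analysis with post-randomisation losses that may depend on treatment and prognosis, and its sections disagree on when follow-up ends and which events end participation. The gap is certain from the text; its size is not. Under the assumed one-sided losses, the bias runs from 0.1 days to about the full 2-day design effect, and it is nil if comparable patients are lost equally. Those figures rest on assumed exit numbers, assumed VFD deficits and the planned SD of 2.9. They show what is possible and do not predict what will happen. The point should be fixed, with medium confidence that it would matter in practice.

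**What to change.** 1. In 4.4 and 7.2, state that stopping study procedures does not stop outcome collection. Ventilator and vital status are collected to day 28 for every randomised patient, except those who withdraw consent to use of their data.
2. Reconcile the Synopsis and 3.3 with 3.1 and 4.4 on when follow-up ends, and 4.4 with the Synopsis and 7.2 on which events end participation. No clinical rule is proposed here; the sections only need to agree.
3. In 6.2, replace the missing-data sentence. The primary analysis includes all randomised patients in their assigned arm. For patients discharged before day 28, status comes from the EMR or one status call. If it cannot be obtained, ventilator status at discharge is carried forward. Best- and worst-case sensitivity analyses cover any VFD still missing.

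Carrying discharge status forward is one of several acceptable conventions and is itself an assumption, so the best- and worst-case analyses should also be run for patients whose status was carried forward. The cost is protocol wording plus a record look-up or one call for each patient discharged before day 28. The sample size does not change.

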6.3 Sample Size and Power

We utilized preliminary data from earlier studies of mechanical ventilation in the obese to establish a baseline. With a mean duration of mechanical ventilation of 7 days with a standard deviation of 2.9 days, we expect the control group to have 21 ventilator free days. We estimate that we could reasonably see an effect in the intervention group that reduces the duration of mechanical ventilation by 3 days. With a power of 80% and alpha=0.05, we would need 16 patients per group, for a total of 32 patients. Would the effect be only a reduction of mechanical ventilation by 2 days, we would need 34 patients in each group for a total of 68 patients. Because the population in our study would be expected to have a lower mean duration of mechanical

ventilation, we anticipate we may find a smaller effect size. Including a possible 10% dropout, we will target a sample size of 76 (38 per group) to safely achieve our goals.

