3.4 Study Population

Inclusion Criteria: Obese adults (BMI ≥ 40) admitted to the MICU at UNC Hospital or the ICU at Vidant Medical Center ECU with acute respiratory failure requiring mechanical ventilation.

Exclusion Criteria:

1. Refusal to give consent by the subject or their LAR
2. Abdominal compartment syndrome
3. Chest tube for pneumothorax
4. Having been on a ventilator for >4 days
5. Suspicion of or known intracranial hypertension
6. Anticipated extubation within 24 hours
7. Chronic ventilator dependence
8. Condition that precludes placement of an esophageal balloon (esophageal or nasopharyngeal pathology preventing insertion of the esophageal balloon catheter, severe thrombocytopenia or coagulopathy)
9. Incarceration
10. Not expected to survive >48 hours
11. Unable to obtain consent from subject or LAR
12. Unable to obtain consent due to a language barrier

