5.2 Other measurements

Variable	Source	How Measured	Baseline	Daily	Completion
Outcomes					
Ventilator free days at day 28 (Primary outcome)	EMR	Days alive and free of the ventilator			X
Reintubation	EMR	Intubated within 72 hours of extubation		X	X
ICU Length of Stay	EMR	Days			X
Hospital Length of Stay	EMR	Days			X
Tracheostomy	EMR	Y/N			X
Extubation prior to meeting established criteria	EMR	Y/N			X
Highest RASS	EMR	-5 to +4 (single highest value used)	X	X	
Lowest RASS	EMR	-5 to +4 (single lowest value used)	X	X	
Exposures					
Esophageal pressure (Pes)	Ventilator	cm H ₂ O	X	X	
Airway pressure (Paw)	Ventilator	cm H ₂ O	X	X	
Transpulmonary pressure (Ptp) (inspiratory and expiratory)	Ventilator	cm H ₂ O	X	X	
PEEP	Ventilator	cm H ₂ O	X	X	
Opioids	EMR	Continuous, bolus sch, bolus prn, oral sch, oral prn	X	X	
Propofol	EMR	Y/N	X	X	
Dexmedetomidine	EMR	Y/N	X	X	
Benzodiazepines	EMR	Continuous, bolus sch, bolus prn, oral sch, oral prn	X	X	
Antipsychotics	EMR	Sched, PRN	X	X	
Neuromuscular blockade	EMR	Y/N	X	X	
Corticosteroid use	EMR	Y/N	X	X	
Fluid Balance	EMR	Net fluid balance prior to extubation		X	
Safety Measures					
Vasopressor requirement	EMR	norepinephrine equivalents(9)	X	X	
Pneumothorax	EMR	Y/N	X	X	
Other Variables of Interest					
Age	EMR	Years	X		
Race/Ethnicity					
BMI	EMR	kg/m ²	X		
Partial Pressure of Oxygen (PaO ₂)	EMR	mmHg	X	X	
Oxygen Saturation (SpO ₂)	EMR	%	X	X	

PaO ₂ /FiO ₂ ratio	Calculated	Number	X	X	
SpO ₂ /FiO ₂ ratio	Calculated	Number	X	X	
Charlson Comorbidities	EMR	Y/N	X		
Waist circumference	EMR	cm	X		
CAM-ICU	EMR	Positive/Negative	X	X	
SOFA	EMR	Calculated	X		
COVID (y/n)	EMR	Y/N	X		

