6 STATISTICAL CONSIDERATION

6.1 Primary Endpoint

The primary outcome is the number of ventilator-free days (VFD), defined as the number of days alive and ventilator-free by day 28. The assessment of the primary outcome will be conducted by a study team member after subject completion in the study. In order to minimize potential bias, this team member will be blinded to treatment arm assignment.

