7.3 Data and Safety Monitoring Board (DSMB)

We will utilize the NC TraCS DSMB for additional regulatory monitoring of the study. The DSMB will review aggregate safety data after enrollment of 25, 50, and 75% of the study participants. There will be several criteria for evaluating safety and possible early stopping of the trial. Adverse events will be graded based on the CTCAE criteria listed above (7.2 AE Reporting).

- 1) Pneumothorax – If 2 out of 10, or if more than 10 enrolled, 20% out of enrolled subjects experience pneumothorax, then the study will be suspended until the DSMB can review the information and provide recommendations.
- 2) Hypotension – If 2 out of 10, or if more than 10 enrolled, 20% out of enrolled subjects experience refractory hypotension, then the study will be suspended until the DSMB can review the information and provide recommendations.
- 3) Death – If 8 out of 10, or if more than 10 enrolled, 60% out of enrolled subjects die, then the study will be suspended until the DSMB can review the information and provide recommendations.

There are no stopping rules for efficacy, as there will be no interim efficacy analyses. The study is only adequately powered to detect an efficacy difference if it were completed.

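### Section 6.3 sizes the trial on ventilation duration, but deaths also lower 28-day ventilator-free days, so the stated 80% power for a 2-day effect needs essentially no deaths

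*Combined protocol and SAP*

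**What the plan says.** Section 6.1 makes VFD the primary outcome, "defined as the number of days alive and ventilator-free by day 28", and the table in 5.2 measures it as "Days alive and free of the ventilator". Section 6.2 sets the test: "the primary outcome will be analyzed with a 2-sided independent t-test".

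Section 6.3 starts from a different variable, duration of mechanical ventilation, with mean 7 days, and goes on "with a standard deviation of 2.9 days, we expect the control group to have 21 ventilator free days". It then gives 16 per group for a 3-day reduction in duration and 34 per group for a 2-day reduction, at 80% power and alpha 0.05. On the size of effect it adds that "we anticipate we may find a smaller effect size". A 10% dropout allowance takes 34 to 38 per group, 76 in total. Section 7.3 later says: "The study is only adequately powered to detect an efficacy difference if it were completed".

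Deaths are foreseen. Section 4.4 says "Participants will complete the study at the time of death or the conclusion of 28 days, whichever occurs first", and 7.3 has a rule that suspends the study if too many participants die. The only survival-related exclusion in 3.4 is "Not expected to survive >48 hours".

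**The concern.** VFD equals 28 minus duration only in a patient who is alive at day 28. Someone ventilated for 5 days who dies on day 5 has a short duration and no ventilator-free days. Deaths therefore add a low tail to VFD that the duration SD of 2.9 does not contain. Even a few values near 0 among values near 21 inflate the variance sharply, and the t-test loses power accordingly.

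The dropout allowance does not cover this. A patient who dies is not missing: the endpoint is defined for that patient, and the value is low.

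The 2-day scenario sets the target of 76. If its power is well below 80%, a real 2-day benefit would end as an inconclusive result (the label in 6.2 for p above 0.05) far more often than the implied 20%. Readers relying on 6.3 and 7.3 would misjudge what the completed trial can detect.

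**Working it through.** **Inputs from the documents.** Two-sided t-test, alpha 0.05, 80% power, 1:1 allocation; duration mean 7 and SD 2.9; effects of 3 and 2 days; 10% dropout; 38 per arm.

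**Step 1: reproduce 6.3.** The exact two-sample t-test calculation gives 15.7, so 16 per arm, for 3 days with SD 2.9, and 33.99, so 34 per arm, for 2 days. Then 34/0.9 = 37.8, so 38 per arm. All three figures match. Power for 2 days is 80% at 34 per arm and 84% at 38. The arithmetic is right; the SD belongs to another variable.

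**Step 2: add deaths.** Assumptions not in the documents: the same mortality m in both arms; survivors' VFD mean 21 versus 23, SD 2.9. With deaths scored 0:

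- mean difference = 2(1 − m)
- variance in an arm with survivor mean μ = (1 − m) × 2.9² + m(1 − m) × μ²

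For m = 5%:

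- difference = 2 × 0.95 = 1.9
- control variance = 0.95 × 8.41 + 0.0475 × 441 = 7.99 + 20.95 = 28.94
- intervention variance = 7.99 + 0.0475 × 529 = 7.99 + 25.13 = 33.12
- averaged SD = √31.03 = 5.57, nearly double 2.9
- power = 28% at 34 per arm and 31% at 38

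For m = 10%, the difference is 1.8, the SD 7.16 and power 18% and 19%.

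**Step 3: simulate the planned t-test under both scorings.** Duration is Normal (7 or 5, SD 2.9), cut to 0–28, and deaths occur independently with probability m. A death scores either 0 or the ventilator-free days before it, with day of death uniform over 0–28. There were 20,000 trials per scenario. Power ranges run from 34 to 38 per arm. The detectable difference is the mean VFD difference with 80% power at 38 per arm, from the t-test formula and the unrounded simulated SD.

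| Mortality, both arms | Deaths = 0: power | VFD SD | Detectable (days) | Earlier days count: power | VFD SD | Detectable (days) |
|---|---|---|---|---|---|---|
| 0 | 80–84% | 2.9 | – | 80–84% | 2.9 | – |
| 1% | 64–67% | 3.6 | 2.3 | 71–76% | 3.2 | 2.1 |
| 2% | 52–55% | 4.2 | 2.7 | 64–68% | 3.5 | 2.3 |
| 5% | 32–35% | 5.5 | 3.6 | 49–52% | 4.3 | 2.8 |
| 10% | 19–21% | 7.1 | 4.7 | 34–36% | 5.3 | 3.5 |
| 20% | about 12% | 9.2 | 6.0 | 22–24% | 6.7 | 4.4 |

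The formula in step 2 runs a few points below the simulation, because it applies normal-theory power to a skewed mixture. With deaths at 0, a gamma distribution for duration with the same mean and SD gave power within about 1.5 points of the Normal.

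**Step 4: other scenarios.**

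- Exactly one death in each arm of 38: power about 40% if scored 0, 63% if earlier days count.
- 3-day effect at 10% and 20% mortality: 33–36% and 18–20% (deaths at 0); 60–64% and 40–43% (earlier days count).
- Mortality benefit, 20% versus 10%, plus 2 days in survivors: 50–54% (deaths at 0); 59–64% (earlier days count).

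**The case against.** **The definition can be read literally.** Sections 5.2 and 6.1 describe a count of days, and nothing there sets a death to 0. On that reading, ventilator-free days lived before death count, and the right-hand power column applies. This is fair, and it softens the loss, but power is still 49–52% at 5% mortality. An explicit rule is needed because the same patient could otherwise be given different values.

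**The inputs are assumed.** Mortality, uniform timing of death, and independence of death from duration are not in the documents. Uniform timing from day 0 is somewhat pessimistic given the 48-hour exclusion. The 60% death figure in 7.3 is a suspension trigger, not an expected rate. It also cannot be seen whether the source studies for the SD of 2.9 included patients who died. All of this stands, so no single power figure can be claimed. The direction and the early loss of power do not depend on the exact mortality.

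**The intervention may save lives.** That raises power, but the benefit must be substantial. In a check run, 20% versus 5% mortality plus 2 days gave 80–87%, whereas 20% versus 10% stays below 80%.

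**The 3-day effect has spare power.** With deaths at 0 and 34 to 38 per arm, it keeps 77–81% at 2% mortality but only 54–58% at 5%. Section 6.3 itself expects a smaller effect, and the 2-day case sets the target.

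**Limited harm.** Type I error and the effect estimate are not affected, 6.2 already calls a non-significant result inconclusive, and the sentence in 7.3 mainly explains why there is no interim efficacy analysis. These points limit the consequences; they do not make the power statement correct.

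**Conclusion.** The concern holds and must be fixed. The 80% power in 6.3 belongs to duration in patients who all survive to day 28, not to the t-tested endpoint of 6.1. The plan contains neither the mortality nor the VFD SD needed to read off the real power.

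At equal mortality of 1% or more, power for the 2-day effect is below 80% under both scorings and at both 34 and 38 per arm. Across 5% to 10% mortality it runs from about 52% down to 19%, depending on the rate and the scoring. The sizes rest on assumed mortality, survivors' SD 2.9, death independent of duration and, where earlier days count, uniform death times. Only a substantial mortality benefit would restore 80%.

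**What to change.** 1. In 6.1, state how a death by day 28 is scored: 0, or the ventilator-free days lived before death.
2. In 6.3, state the assumed 28-day mortality and a VFD SD that includes deaths, with its source, then restate power and the detectable difference. For example: assuming x% mortality in both arms and a VFD SD of y days, 38 per arm gives z% power for a 2-day reduction in ventilation among survivors. Show a small range if mortality is uncertain.
3. In 7.3, bring the sentence on adequate power into line with 6.3.

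All three are wording changes. They ask for no extra patients; the cost is a less favourable stated power.

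One option for the sponsor to weigh is a Wilcoxon rank-sum test on VFD as scored in 6.1, with deaths not re-ranked, as the primary test, keeping the mean difference and its confidence interval as the effect size. With deaths at 0 and the same assumptions, its power for the 2-day effect is 60–64% at 10% mortality and 39–44% at 20% (6,000 trials per scenario, type I error 4.4–5.5%). The trade-off is real: the p-value would no longer test a mean difference. If the only effect were on mortality (20% versus 10%), the rank test would have about 11% power against 19–20% for the t-test.
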